#### B. Effects of Additional Procedures

##### **Skin Biopsies**

The risk of skin biopsy may be slight bleeding or infection. To avoid these complications a sterile dressing will be applied for 7-10 days until the scar is well formed. On occasion, the wound may be closed with 1 or 2 non-absorbable sutures. Acquiring skin fibroblasts from voluntary subjects is minimally invasive. Skin biopsy procedures can be considered as minimal risk since the risk is not greater than blood draws, a procedure already included in the protocol. The level of discomfort associated with the anesthesia is analogous to a PPD skin test for TB and the biopsy itself is painless.

### **Blood Drawing**

One discomfort of this study may occur due to the venipuncture and multiple blood sampling. Total blood withdrawal (550-660 ml) falls within NIH guidelines (550 ml. per eight week period during this 20-24 month study).

#### **8) Subject Safety Monitoring:**

Subjects are evaluated by one of the associate investigators. Medical history and physical assessments occur at each clinic visit including interviews, symptom assessments, vital signs, and laboratory testing when clinically indicated. After completing the study, subjects will either be discharged from this protocol with a referral to the community, or will be referred to other NIMH studies.

Patients will be warned not to become pregnant during the study and will be advised to employ barrier contraceptive methods.

#### **9) Outcome Measures:**

The outcome measures are as follows: 1) brain imaging measures including O PET and fMRI (performed as part of NIMH protocol 90-M-0014); 2) Dex/CRH stimulation tests; 3) metabolomic profile; 4) DNA for genotyping (performed under protocol 81-M-0126; and

5) cell culture studies (lymphoid and IPCs). Additionally, we will employ the symptom ratings (described above) to evaluate the effects of GnRH-agonist-induced hypogonadism and estradiol and progesterone replacement on measures of mood and behavior.

10) Statistical Analysis:

In this protocol we originally proposed using 30 subjects. Calculations of the minimum sample size that will provide statistical significance between the three different hormonal states (hypogonadal, hypogonadal plus estrogen, and hypogonadal plus progesterone) with a power of 80% were performed using the results obtained in the Hampson and Kimura study (190). Additionally, we supplemented this analysis with our own preliminary neuropsychological testing results from protocol # 90-M-0088. In the Hampson and Kimura article standardized differences of 0.6, 0.7, and 0.5, were calculated for the finger tapping, Purdue Pegboard, and the manual sequence box, respectively. The standardized difference obtained from five women who have been tested during the hypogonadal and during the hypogonadal plus estrogen phase of protocol # 90-M-0088 results in a standardized difference of .6. Thus, the originally calculated sample size required to provide 80% power at an alpha of 0.05 with the standardized difference obtained from these two investigations was approximately 30 subjects.

Amendments to Sample Size

Brain Imaging

On the basis of our prior work (65), and as described in protocol # 90-M-0014 we anticipate that the 20 subjects recruited for the HPA axis studies will be ample for showing differences in rCBF.

Skin Biopsies

To recruit sufficient numbers of women in each group we will contact women who have

previously participated in these protocols, have met our baseline criteria for PMD or asymptomatic controls, and have further demonstrated either the elimination of symptoms during GnRH agonist and return of symptoms upon re-exposure to estradiol or progesterone (PMD) or the absence of negative behavioral symptoms during both GnRH agonist and ovarian steroid addback phases (controls). Each of these women who is interested in participating will be re-consented for this study.

11) Human Subjects Protection:

a. **Subject selection**

All subjects must meet the inclusion and exclusion criteria listed in Section 6. We will select physically healthy adult female individuals. The proportion of ethnic minorities (vs. Caucasians) in the total sample, will be approximately consistent with the overall U.S. population proportions.

We are limiting the upper age range of the women in this study to 50 years of age to match the age ranges with those in the existing companion protocols, 90-M-0088 and 05-M-0059. Women over the age of 50 may have age-related changes in brain function, HPA axis function, or reproductive hormone secretion, which could have confounding effects on the outcome measures in this and the companion protocols.

b. **Justification for exclusion of children**

We will exclude children or minors because the study population is menstruating premenopausal women.

c. **Justification for exclusion of other vulnerable subjects**

We will exclude subjects that are unable to provide their own consent given the length of the protocol and associated risks.

**d. Justification of sensitive procedures** N/A

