**Medical Advisory Investigator**

Total requested accrual

0 Patients

150 Volunteers

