The objectives of this study are to examine the effects of hypogonadism with and without physiologic replacement of estradiol and progesterone on measures of brain function and behavior. The use of GnRH agonists to suppress ovarian function (hypogonadism) permits us to examine the effects of estradiol and progesterone on brain function separately, and to standardize the exposure to these hormones across individual women and in our comparison in women with premenstrual dysphoria (PMD), who participate in an identical companion protocol (90-M-0088). The outcome measures currently employed in this study are as follows: 1) brain imaging with  $^{15}\text{O}$  PET and fMRI to examine brain activation and connectivity and the impact of genomic variation on these neuroimaging measures; 2) HPA testing with Dex/CRH stimulation; 3) metabolomic profile of neurosteroid and neuroactive steroid metabolites, and 3) cell culture studies (lymphoid and IPCs) to examine cellular responses to exposures to ovarian steroids in controls and women with PMD (90-M-0088).

3) Subjects:

a) Description of study populations

Healthy asymptomatic premenopausal women with no current Axis I diagnosis and no evidence of menstrual-related mood or behavioral disturbances. The targeted accrual of 150 women reflects the use of this protocol to examine specific goals that have developed over the course of this protocol.

b) Inclusion criteria

Volunteers participating in this study will be women meeting the following criteria:

- between the ages of 18 and 50 years,
- not pregnant,
- in good medical health,
- medication free,
- no history of menstrual-related mood or behavioral disturbances.

Additionally, we will recruit a subsample of 20 asymptomatic women who will meet all inclusion and exclusion criteria in this protocol except they will have a history of a past major depressive episode.

Finally, a sample of 10 women who meet all the inclusion and exclusion criteria listed above for this protocol will be recruited to establish the dose range of transdermal .36% estrogen gel for this and related protocol (i.e., 90-M-0088).

c) Exclusion criteria

The following conditions will constitute contraindications to treatment with hormonal therapy and will preclude a subject's participation in this protocol:

- Current Axis I psychiatric diagnosis (with the exception of those women with a past major depression who will be studied in this protocol);
- History consistent with endometriosis;

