GnRH agonist will not be administered to any subject with significant clinical or laboratory abnormalities.

Additional tests.

Results of Pap smear performed not longer than 12 months prior to onset of treatment will be obtained.

d) Study Procedures

Medications:

Following the baseline screening period, subjects will be administered 3.75 mg of GnRH agonist via intramuscular injection on a monthly basis in our clinic for a maximum of 24 weeks (see Figure I).

After week eight of GnRH agonist treatment participants will be randomized to either Group # 1 or # 2 and receive, in a sequential fashion, estradiol and progesterone as follows. The subjects who elect to participate in the brain imaging studies will receive three months of Lupron alone (rather than two) to permit their data to be compared with those from protocol # 90-M-0088. Consequently, subjects in the brain imaging studies will be randomized to Groups 1 or 2 after week 12 of Lupron alone.

Group # 1: (Figure 1) While continuing on the GnRH agonist, subjects will be administered 0.1 mg/day of 17 $\beta$ -estradiol once or twice a day via vaginal suppository for a period of five weeks. After the fourth week, progesterone suppositories (200 mg BID) will be added to provide progesterone withdrawal induced shedding of the endometrium and menses in order to prevent any effects on the endometrium of prolonged exposure to unopposed estrogen. After the four weeks of estradiol administration and the one week of combined estradiol and progesterone, there will be a two week washout period when neither estradiol nor progesterone will be given.

Subjects will then be administered progesterone suppositories (200 mg) twice daily for a period of five weeks after which no progesterone will be taken.

Group # 2: Group # 2 is identical to Group # 1 except that the order of estradiol and progesterone treatments will be reversed: progesterone suppositories (200 mg) will be administered twice daily for the first five weeks, and after a two week washout period estradiol suppositories will be administered for five weeks and in combination with progesterone during the fifth week.

Symptom Ratings:

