estradiol levels targeted in this study (i.e., 80-120 pg/ml). If after one week of two applications of estradiol gel once a day, we observe that this dose schedule is insufficient to consistently obtain the desired blood levels, we will increase the dose to three applications (9.0 mg) each day for the next three weeks. Alternately, if adequate blood levels are observed after the two applications once a day regimen then women will continue at this dose for the remaining three weeks to evaluate the stability of plasma estradiol levels with the two applications each day regimen. We do not anticipate needing a dose greater than three applications each day. After the four weeks of estradiol treatment, all women will receive one week of progesterone suppositories (200 mg twice a day) to precipitate a progesterone withdrawal-induced menses. Upon completing this evaluation, we will provide the data to the FDA to modify the IND under which this protocol and its companion protocol (90-M-0088) are conducted. The duration of Lupron treatment is a third the length of time in which Lupron is administered in the regular six month protocol and the duration of estradiol treatment is the same as that approved in the original protocol. Women participating in this component of the protocol will not be asked to participate in any of the additional procedures employed in the six month protocol (i.e., brain imaging, IPCs, or metabolomics).

Blood Samples for this component of the protocol (10 ml) will be drawn at each visit, if possible, for the duration of the study (8 weeks). Total blood volume will be 90 ml. All blood sampling will be obtained as described in the core protocol. This blood will then be analyzed for gonadotropins and estradiol.

e) End of Participation

When available, the results of this study will be discussed with each participant. Controls

will be discharged from this protocol with follow-up as needed by their private healthcare provider.

5) Management of Data and Samples:

a. Storage

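### Does the accrual of 150 women fail to add up, and are the genotype and reward questions left without a sample size?

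*Combined protocol and SAP*

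**What the plan says.** The front matter of the combined protocol and SAP requests "150 Volunteers". Section 3a explains the figure in one sentence: "The targeted accrual of 150 women reflects the use of this protocol to examine specific goals that have developed". It gives no breakdown.

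Four planned groups carry a number:

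- Section 10 begins "In this protocol we originally proposed using 30 subjects", sized for 80% power at alpha 0.05 on motor and neuropsychological tests.
- Section 10, Amendments to Sample Size, Brain Imaging: "we anticipate that the 20 subjects recruited for the HPA axis studies will be ample for showing differences in rCBF". It cites earlier work and protocol 90-M-0014.
- Section 3b: "we will recruit a subsample of 20 asymptomatic women" with a past major depressive episode.
- Section 3b: "a sample of 10 women who meet all the inclusion and exclusion criteria listed above", for the estradiol gel pilot. Section 4d, part B, adds: "Women participating in this component of the protocol will not be asked to participate in any of the additional procedures".

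The skin-biopsy paragraph in Section 10 gives no number. Section 4d, Medications, treats imaging as optional: "The subjects who elect to participate in the brain imaging studies will receive three months of Lupron alone".

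The precis asks three questions: whether the earlier prefrontal blood-flow finding is confirmed, whether genotype alters sensitivity to ovarian steroids, and whether reward-system changes are due to estradiol or progesterone. Section 9 places the PET and fMRI work under protocol 90-M-0014 and genotyping under 81-M-0126. Section 14c lists three consent forms: standard six-month, estradiol gel, and major depressive episode.

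**The concern.** A reader who adds up the stated groups reaches 80 and finds nothing that leads to 150. The amendments heading in Section 10 is where the step should be explained, yet it goes from 30 to 20 and never mentions 150. The imaging sentence covers regional cerebral blood flow only. It is a within-woman comparison of hormone states, so it does not carry over to the genotype question, which compares women with each other.

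This would matter because the study is classed as more than minimal risk, offers participants no direct benefit, and gives up to 24 weeks of ovarian suppression. If nearly half the accrual served no sized objective, the number exposed would be hard to defend. If only about 20 women were imaged and genotyped, the genotype question could detect only very large differences.

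**Working it through.** **1. The plan's own figure.** Inputs from Section 10: standardized differences of 0.5, 0.6 and 0.7, power 80%, alpha 0.05. The documents do not say whether the test is two-sided or adjusted, so both are tried. For a within-woman comparison, n = ((z for alpha + z for power) / d)², rounded up:

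| d | two-sided 0.05 | two-sided 0.05/3 (three state comparisons) |
|---|---|---|
| 0.5 | 32 | 42 |
| 0.6 | 22 | 30 |
| 0.7 | 17 | 22 |

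For example, ((1.960 + 0.842)/0.5)² = 31.4, so 32. With the t distribution, d = 0.5 unadjusted needs 34, and d = 0.6 at 0.05/3 needs 32. The stated figure of approximately 30 is reproduced, although the variant used is not given.

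**2. The sum.** With no overlap, 30 + 20 + 20 + 10 = 80, and 150 − 80 = 70, which is 70/150 = 47%. If the 20 HPA women are among the original 30, the sum is 60, and 90 women (60%) remain.

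**3. Where the rest belong.** Section 14c has three consent forms. Section 3b sizes two of the groups they serve: past depression at 20 and gel at 10. On that reading the standard six-month form covers 150 − 20 − 10 = 120 women, among them the 30 and the 20. So the 70 (or 90) have a place in the study; what they lack is a stated reason for their number.

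The documents also name work with no counts attached: the exercise-stress and m-CPP studies (Sections 1B and 1C), the suppository and 0.06% gel pilots (Section 1D), and Dex/CRH testing, metabolomics and cell culture (Sections 2 and 9). The 80 is therefore the sum of the groups that happen to carry a number, not a stated breakdown of the 150.

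**4. The 20 for blood flow.** With 20 women, a paired t-test (two-sided 0.05, 80% power) detects a standardized difference of 0.66; power at 0.6 is 72%. The protocol gives no rCBF difference or SD, so the claim that 20 is enough can be neither reproduced nor refuted. The sentence reuses an existing group. Section 3 lists eligibility groups, not procedures, and women in the HPA studies can elect imaging, so there is no conflict with Section 4d.

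**5. The genotype question.** This illustration assumes the genotype splits, a two-sample comparison of within-woman change, two-sided 0.05 and 80% power. With 20 women the detectable difference is 1.32 SD (10/10) or 1.53 SD (5/15). At an assumed 0.6 SD, power is 25% or 20%. Twenty women would be few, but the plan does not say that 20 is the number for this question. Nor does it give any other number: taking all 150 − 10 = 140 non-gel women as imaged would contradict the elective nature of imaging.

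**6. The imaging protocol number.** It is 90-M-0014 in Sections 9 and 10 and 90-CC-0014 in Section 4d, Blood Samples. This is a clerical mismatch with no effect on the analysis.

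**The case for a change.** The strongest case for a change is ethical. Healthy volunteers take on more than minimal risk with no direct benefit, so the number exposed should have a stated basis. One sentence about goals that developed over time is not a calculation. The original 30 was sized on motor and cognitive tests that are not among the five outcome measures in Section 9, and the imaging aims listed first there have a number for blood flow only. An allocation table would cost little and add no subjects.

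Part of this stands. Section 10 does not justify the step to 150, and this document gives no number for the genotype and reward questions. A table would make the protocol easier to read.

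The rest is weaker. The 30 is presented as historical, and cognitive batteries are still given at four time points (Section 4d, Blood Samples). Sizes for imaging and genotyping may lie in the linked protocols, which are not available here; Section 10 cites the imaging protocol for the blood-flow size. The precis poses genotype as a question and claims no confirmatory test, so requiring an exploratory label would be a preference. Lowering the accrual would be a trade-off, since the documents do not show that 150 is too many.

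**Conclusion.** No change to the plan follows. The arithmetic is correct: at most 80 of 150 women are in groups with a stated number, leaving 70 (47%), or 90 (60%) if the 20 lie within the 30. It shows missing explanation, not an error. About 30 reproduces, the 20 for rCBF is not contradicted by any figure in the documents, and no analysis or estimate would come out wrong if the plan were followed as written. The main remedy would be to write down an allocation that the investigators presumably hold.

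This rests on two readings: that the remaining women belong to the standard six-month study, as the three consent forms suggest, and that the linked protocols govern the size of the imaging and genotype work. The first is an inference; the second cannot be checked here. If those protocols proved to give no size, the genotype results would have to be read with the limited precision shown above for about 20 women.

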**e. Safeguards for vulnerable populations**

Protections for NIH employees and staff participating in this study include 1) assuring that the participation or refusal to participate will have no effect, either beneficial or adverse, on the subject's employment or position at the NIH, 2) giving employees and staff who are interested in participating the "NIH Information Sheet on Employee Research Participation" prior to obtaining consent, and 3) assuring that there will be no direct solicitation of employees or staff.

Screenings are performed by [name], who is a licensed social worker in our group, and who is in charge of our recruitment and outreach activities. Personally identifiable information is not obtained in callers who are determined to be ineligible, and the screening forms are not retained in the research records.

12) Anticipated Benefits:

There are no direct benefits to participants in this protocol. This protocol allows us to selectively examine the central nervous system effects of the gonadal steroids and, thus, provides

the opportunity to explore the linkages between changes in mood and behavior and gonadal steroid activity. Further, as a control for protocol # 90-M-0088 this study will extend our understanding of potential biological mechanisms underlying menstrual-related mood disorders and offers the possibility of uncovering some etiopathogenic mechanisms involved in these and related mood disorders.

13) Classification of Risk:

The overall risks for this study are more than minimal.

There are low risks to individual subjects in the use of medication and procedures under the conditions stated in this protocol.

14) Consent Documentation and Process:

a. Designation of those obtaining consent

Study investigators designated as able to obtain consent in section 12 above, will obtain informed consent.

b. Consent procedures

Each patient will receive a verbal and written explanation of the purpose, procedures, and potential hazards of this project. A record of the communication of this information and of the consent to participate in this study will be placed in the medical record. The right of the subjects to withdraw from the study or to refuse any procedure will be made clear. Any patient whose side effects become excessive during either the GnRH alone or estrogen/progesterone replacement phases will be offered the option to withdraw without completing the five or six month trial. Confidentiality of patients will be assured according to the laws of the State of Maryland. In case of published data resulting from the study, care will be taken to protect the anonymity of patients.

c. Consent documents

Each consent contains all required elements. There are 3 consent forms used for this protocol: Standard (6 months), Estradiol gel (pilot study), and MDE (major depressive episode).

15) Data and Safety Monitoring

a) Data and safety monitor

The PI will serve as the data and safety monitoring official.

b) Data and safety monitoring plan

As we are administering doses of estradiol and progesterone designed to produce physiologic levels, we expect - and have seen - no unexpected adverse events. Similarly, we do not anticipate unexpected serious adverse events with the dose of Lupron that we propose to use. Nonetheless, we see subjects every one to two weeks during their clinic visit and advise them in the consent form that if they experience side effects, they should notify the investigator immediately. Any adverse events will be reported as per NIH policy. The PI will review data and safety parameters at least annually. The PI will document the data and safety review in the research records and at the time of continuing review.

c) Criteria for stopping the study or suspending enrollment or procedures

The study will be stopped if the estradiol suppositories become unavailable or if new findings emerge that indicate it would not be safe to continue the study. The study will be stopped if there is any Serious Adverse Event related to the research.

The PI and IRB will determine if changes are needed for the research to continue or if it will be closed.

16) Quality Assurance:

A. Quality assurance monitor

Quality assurance will be monitored by the PI, the research team and the NIMH Office of Regulatory Oversight (ORO).

B. Quality assurance plan

ORO monitors intramural research studies to ensure compliance with GCP, organizational policies and regulations. Audit frequency is determined by the ORO SOP based on the study level of risk. Results of ORO audits are provided to the PI, The Clinical Director and the CNS IRB. As an IND study, this protocol will be subject to GCP audits at study initiation and after the first enrolled subject. Timing of subsequent review will be established by ORO but no less frequent than every other year.

17) Reporting of Unanticipated problems, adverse events and protocol deviations:

The Principal Investigator is responsible for detecting, documenting, and reporting unanticipated problems, adverse events (AEs), including serious adverse events (SAEs), and deviations in accordance with NIH policy, IRB requirements, and federal regulations. Relatedness to the research of all serious adverse events will be determined by the PI in consultation with the CD.

Serious unanticipated problems, serious adverse events (including deaths) that are not unanticipated problems, and serious protocol deviations will be reported to the IRB and CD as soon as possible and in writing not more than 7 days after the PI first learns of the event, unless immediate reporting is waived for specific serious adverse events as noted below. Not serious unanticipated problems and not serious deviations will be reported to the IRB and CD as soon as possible and in writing not more than 14 days after the PI first learns of the event. Written reports will be submitted in PTMS.

All adverse events, deviations, and unanticipated problems will be summarized and reported at the time of Continuing Review.

18) Alternatives to Participation:

Subjects do not receive any treatment in this study or forego any treatment in order to participate in this study. The alternative, therefore, is not to participate.

19) Privacy

All research activities will be conducted in as private a setting as possible.

20) Confidentiality

a. For research data and investigator medical records

Samples and data will be stored using codes that we assign. Data will be kept in password-protected computers.

No sensitive information is collected, so employee information will be treated the same as all other participants.

b. For stored samples

Samples will be kept in locked storage. Only study investigators will have access to the samples and data. Samples and data will be stored using codes that we assign. DNA samples and cell lines will be stored in locked freezers in [name]'s laboratory (NIAAA) on [name]. Only study investigators will have access to the samples and data.

c. Special precautions: N/A

21) Conflict of Interest

a. Distribution of NIH guidelines

NIH guidelines on conflict of interest have been distributed to all investigators.

b. Conflict of interest

There are no conflicts-of-interest to report.

22) Technology Transfer

There is an active CTA with Besins Healthcare which was executed on 08/01/14 and expires on 08/01/19. Samples and data will be stored using codes that we assign. Data will be kept in password-protected computers. Samples will be kept in locked storage. DNA samples and cell lines will be stored in locked freezers in [name]'s laboratory (NIAAA) on [name]. Only study investigators will have access to the samples and data.

23) Research and Travel Compensation:

Each volunteer will be compensated according to the following schedule:

Core Protocol

Initial evaluation, physical exam (2 hours)	100.00
Screening phase	100.00
Clinic visits (weekly) 2 hour x 13	390.00
Multiple venipuncture x 13	260.00
Psychological testing x 13 (at each clinic visit)	100.00
Symptom rating scales x 6 months	150.00
Investigational drugs	
a) Depot Lupron injections 100.00 x 6	600.00
b) Vaginal suppositories/transdermal patch daily x 3 months	800.00
Total	2500.00

Dose-finding protocol for estradiol gel:

Initial evaluation, physical exam (2 hours)	100.00
Screening phase	100.00
Clinic visits (weekly) 2 hour x 7	210.00

Multiple venipuncture x 9	180.00
Symptom rating scales x 2 months	50.00
Investigational drugs :	
a) Depot Lupron injections 100.00 x 2	200.00
b) Estradiol gel application daily x 1 month	60.00
Total	900.00

Reimbursement of travel and subsistence will be offered consistent with NIH guidelines.

Compensation will be prorated for parts completed if subjects do not complete the study. No escort fee will be provided.

Employees and staff who participate during work hours must have permission from their supervisor. NIH employees must either participate outside of work hours or take leave in order to receive compensation.

